8.9 Neuromuscular electrical stimulation (NMES)

Participants randomised to the NMES group will receive NMES at each dialysis session they attend for 3-months. It will be administered using a commercially available 4-channel portable stimulator with participants either sitting or laid down (however they are usually positioned for dialysis). The skin will be cleaned and then electrodes will be placed upon the thigh muscles. The participants will have control of the NMES device on which they will be able to change the current that is administered. During the first two to three sessions participants will be encouraged to find their initial comfortable level of stimulation intensity (the current) and to get used to how it feels. After the first week the training will be progressed by two methods:

- 1. Increasing session duration up to a maximum of 30 minutes, if this is not initially achievable (excluding warm up and cool down)
- 2. Increasing stimulation intensity (current) which determines the strength of the muscle contraction that is induced and therefore how uncomfortable it can feel.

Participants will be encouraged to increase the stimulation intensity beyond their initial comfortable level for a portion of each session. As participants become increasingly familiar with NMES and as they adapt they will be encouraged to progressively increase the stimulation intensity further. This progression will also be guided by their individual rating of perceived exertion (RPE). RPE is a scale that guides exercise intensity. Participants will be familiarised with this in the first few NMES sessions. Participants will be encouraged to achieve a of about '4' or 'somewhat' hard. In addition, a discomfort scale will be shown to the participants to help ensure the stimulation intensity is at the correct level. Exercise intensity will also be monitored through a session using a heart rate monitor to measure heart rate and blood lactate concentrations will be measured at the end of the session. Both of these will be performed once a month to more closely monitor progress.

Heart rate monitor: A heart rate strap will be placed around the middle of the chest and a watch placed on the participants wrist to measure heart rate over the course of the NMES session.

Blood lactate testing: This will be performed at the end of the NMES session using the needle prick technique. Briefly, the skin on the finger (any finger can be used, but preferably the index finger) is cleaned and a single use finger prick needle (like the ones used by diabetics for blood glucose monitoring) is used to punch a small hole in the skin. Blood is absorbed onto a lactate strip and entered into the hand-held analysis device.

Every NMES session will be preceded with and followed by a cool down each of 5-minutes duration that will involve a progressive ramp-up/ ramp-down in stimulation intensity, with the warm-up starting at 20% and finishing at 70% of the maximum intensity used by the individual in the previous session, and the cool down vice versa.

8.10 Follow-up assessments

All outcome assessments made at baseline will be repeated at -3, -6 and -9-months post randomisation with the exception of the optional outcome measures which will be performed at baseline and -3 months only.

8.11 Patient Reported Outcome Measures

Questionnaires

Participants will be asked to complete the KDQoL, EQ-5D-5L questionnaire, SONG-HD questionnaire, SARC-F questionnaire, GP Physical Activity questionnaire, SarQoL questionnaire, and a resource use questionnaire, which will be combined into one survey pack.

8.12 Expenses and benefits

Participants will not be paid for their involvement in the study. However, if visits are required that are not part of their normal care their travel expenses will be reimbursed at the usual NHS rate of 45p/mile up to the value of £60 per visit. If a participant requires a taxi then this can be arranged.

8.13 Work Package 3: Health Economic Evaluation

Renal replacement therapy (dialysis and transplantation) is needed by 64,000 people in the UK alone and has a high cost, consuming 1-2% of the NHS budget (56). These high costs necessitate complex economic modelling of renal interventions which alter quality of life, clinical outcomes, dialysis setting and cost, both within and beyond the study. There are no existing health economic evaluations of neuromuscular electrical stimulation programmes in this or any other cohort of patients with long-term health conditions and as the implementation of any such intervention requires institutional support from dialysis providers; providing evidence that such schemes are cost-effective is therefore crucial (57).

8.13.1 Data sources

Resource use, and expenditure data will be collected from a participant self-completed questionnaire at baseline, 3-months, 6-months and 9-months as well as routine clinical databases (UK Renal Registry (UKRR)). To minimise recall bias, participants will be issued with diaries in which to record their healthcare visits and other related resource use and expenditure to aid completion of the aforementioned self-completed questionnaire. This diary will complement the self-completed questionnaire that participants will complete at baseline, 3-months, 6-months and 9-months. Data collected will focus primarily on healthcare-related, NHS costs (i.e. hospital admissions and length of stay, visits to and from healthcare professionals, medication) with a secondary focus on the perspective of patients and carers (i.e. changes in employment, leisure activities and unpaid care of others due to dialysis, associated travel and intercurrent illness). Resource use data will be combined with unit costs using standard validated tools (18-20) to obtain a cost per patient. To validate the healthcare resource use and expenditure data collected from participants, responses for a sample of participants will be compared to routine clinical data from healthcare secondary care records. We will obtain data on set-up and ongoing staff and resource expenditure from participating sites related to the delivery of the intervention (e.g. NMES consumables, any additional staff time, lengthening of dialysis visit etc.).

Calculation of Quality Adjusted Life Year (QALY): The EQ-5D-5L will be used to determine health state descriptions for the five components (mobility, self-care, usual activities, pain / discomfort and anxiety/discomfort) at baseline, 3-, 6- and 9-months and utility values calculated. Utility scores will be derived from participant responses to the EQ-5D-5L at baseline and 1-, 3- and 6- months. UK utility values will be derived using the approach recommended by NICE, which is currently using the validated mapping function from the existing EQ-5D-3L. These will be used to form Quality Adjusted Life Year (QALY) profiles over the 6-month period, adjusting for any imbalances in baseline EQ-5D-5L scores(21).

8.13.2 Cost effectiveness analysis

The difference in resource use, costs and quality adjusted life years (QALY) between the intervention and control arms will be calculated. An intention to treat and per-protocol analysis will be performed (the latter informing the beyond trial model below). This will reflect set-up and per session costs, ultimately reporting the cost per QALY gained; that is, the ratio of the change in costs to the change in QALYs between the 2 groups. Study results will be extrapolated to explore the potential costs and effect over the longer-term.

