2. RATIONALE

The mainstay of treatment for sarcopenia is lifestyle modification, principally exercise interventions. Exercise has been shown to improve muscle mass and strength in people with sarcopenia on haemodialysis (10, 11). Recent national guidelines from the UK Kidney Association, endorsed by the National Institute for Health and Care Excellence (NICE) and led by authors from this group, routinely recommend dialysis unit-based exercise programmes. Unfortunately, although exercise programmes are likely to be more beneficial from both a cardiovascular and a musculoskeletal point of view, as many as 74% of HD patients are unable or unwilling to participate in such programmes (12, 13). In the recently published CYCLE-HD and PEDAL trials (both undertaken by this group), which investigated dialysis unit-based exercise interventions, of the 2835 patients screened, over 2100 were deemed ineligible (12, 13). Many of the patients were severely deconditioned and adherence to the exercise interventions was extremely low (47% of exercise training sessions prescribed were completed and only 18% adhered exactly to the prescription) (14). Therefore, an accessible alternative is clearly needed.

Neuromuscular electrical stimulation (NMES) is a treatment whereby the application of intermittent electrical stimuli generates involuntary muscle contractions, and might serve as an 'exercise mimetic'. This therapy is used widely in physiotherapy rehabilitation programmes (15, 16) and is now being used in clinical settings, including in intensive care units (17). NMES could represent an ideal alternative for people on HD who are unable to exercise and therefore prevent the inevitable decline in muscle mass and strength that leads to sarcopenia.

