11. STATISTICS AND DATA ANALYSIS

11.1 Sample size calculation

No minimal clinically important difference (MCID) has been reported for muscle strength as determined by isometric dynamometry in the CKD population. However, our data have shown that a 10Nm increase in muscle strength was associated with a reduction in 3-year mortality of 5% (54). The data we have used in our sample size calculation come from the improvement in strength that has been previously reported by three previous studies of NMES in haemodialysis patients (27, 30, 33) i.e. a mean strength improvements of 21.7Nm and a mean standard deviation of 47.5Nm. A total sample size of 228 participants (114 per arm) is needed to detect a 21.7Nm (SD 47.5Nm) difference (standardised effect size of 0.5 (moderate)) in change in muscle strength between groups at 3-months with 90% power at the 5% significance level. This will also account for an expected 10% total attrition rate, based on our previous data (15).

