11.3.3 Analysis of primary outcome

The primary analysis will compare the change in muscle strength from baseline to 3-months (i.e. at the end of the intervention period) between randomised groups. The primary analysis will be conducted by intention to treat (ITT) comparing all those randomised to the NMES programme to those who were randomised to standard care. Linear regression with change in muscular strength as the dependent variable, adjusted for baseline value and the minimisation factors (age, time on dialysis), will be used to compare treatment groups, the adjusted mean difference between the treatment arms will be presented with a 95% confidence interval.

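### Protocol section 8.13.2 feeds the beyond-trial cost-effectiveness model from an undefined per-protocol analysis and states no ITT-based version, leaving the extrapolated cost per QALY open to selection bias

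*Protocol*

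**What the plan says.** Section 8.13.2 of the main trial protocol states: "An intention to treat and per-protocol analysis will be performed". A parenthesis then gives the second of these its use: "the latter informing the beyond trial model below". The costing basis and the reported measure follow: "This will reflect set-up and per session costs, ultimately reporting the cost per QALY gained", defined as "the ratio of the change in costs to the change in QALYs between the 2 groups". The section closes with the extrapolation: "Study results will be extrapolated to explore the potential costs and effect over the longer-term".

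The section gives no reason for preferring per-protocol input and does not mention an ITT-based extrapolation. No part of the protocol defines the per-protocol population. By contrast, section 11.3.3 makes the clinical primary analysis ITT, and the economic objective in section 3.2 is a comparison with standard care from an NHS costing perspective.

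**The concern.** Whether a participant counts as per-protocol is settled after randomisation. In the NMES arm it will depend on tolerance, health and attendance. Under section 8.9 participants control the current themselves and may need time to reach the full session length. Section 11.3.2 expects some data to be lost to death, transplantation and withdrawal, and allows for movement between arms. People who keep up NMES are likely to differ from those who stop, so a per-protocol difference in costs or EQ-5D mixes the effect of NMES with that selection. Extrapolation then carries the mixture forward over a longer horizon.

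The population is also a poor match for the stated purpose. Section 8.13 justifies the evaluation by the institutional support that dialysis providers would have to give. A provider bears the set-up cost for people who start and then stop as well as for those who continue.

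Non-adherence is part of the trial's own rationale. For earlier exercise programmes section 2 reports "47% of exercise training sessions prescribed were completed and only 18% adhered exactly to the prescription". Those figures are not for NMES, but they show that exact adherence and partial completion can be far apart. An undefined per-protocol set could therefore mean very different groups.

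**Working it through.** **No plan figure to reproduce.** The protocol states no cost, QALY gain, NMES adherence or per-protocol proportion, so the size of the error cannot be derived from it. What can be checked is the direction, and how far it depends on unknown inputs.

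**Set-up.** Section 8.13.2 counts set-up costs and per-session costs, so let:
- F = set-up cost per person, c = cost per session, S = sessions in 3 months
- a = proportion of the NMES arm that adheres
- s = share of sessions taken by non-adherers
- g = QALY gain in adherers, h = QALY gain in non-adherers
- b = spurious QALY gain from selecting fitter adherers

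ITT cost per QALY = [F + cS(a + (1−a)s)] / [ag + (1−a)h]

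Per-protocol cost per QALY = [F + cS] / [g + b]

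**Inputs, all assumed:** S = 39, g = 0.02, F = £0 or £200, c = £0 or £10, a = 47% to 90%, b = 0 or 0.01. The low end for a borrows the 47% from the exercise figure in section 2. That figure is a share of sessions in a different intervention, so it serves only as a low illustrative value.

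| Case | ITT | Per-protocol | Ratio PP/ITT |
|---|---|---|---|
| 1. a = 0.47, F = 200, c = 10, s = h = b = 0 | 383.30/0.0094 = £40,777 | 590/0.02 = £29,500 | 0.72 |
| 2. As 1, a = 0.90 | 551/0.018 = £30,611 | £29,500 | 0.96 |
| 3. As 1, b = 0.01 | £40,777 | 590/0.03 = £19,667 | 0.48 |
| 4. As 1, F = 0 | 183.30/0.0094 = £19,500 | 390/0.02 = £19,500 | 1.00 |
| 5. As 1, c = 0, b = 0.01 | 200/0.0094 = £21,277 | 200/0.03 = £6,667 | 0.31 |
| 6. Diminishing returns: a = 0.47, s = 0.5, h = 0.8g = 0.016, F = 0, c = 10, b = 0 | 286.65/0.01788 = £16,032 | £19,500 | 1.22 |
| 7. As 6, F = 200 | 486.65/0.01788 = £27,218 | £29,500 | 1.08 |

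**Reading the table.**
- Cases 1 and 2: a set-up cost spread over a larger average gain makes the per-protocol figure look better, and the gap closes as adherence rises.
- Cases 3 and 5: selection of fitter adherers widens the gap.
- Case 4: with no set-up cost, no selection, and gain proportional to sessions, the two figures agree.
- Cases 6 and 7: if partial users get most of the gain from half the sessions, the per-protocol figure is the less favourable one.

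Across a grid with a from 0.47 to 0.90, the values of F, c and b above, s of 0 or 0.3, and h either zero or proportional to sessions, the ratio runs from 0.31 to 1.00. Cases 6 and 7 lie outside that grid.

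**The case against.** Several parts of the opposing case are sound and limit the point.

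- **The extrapolation is exploratory.** The section says only that the per-protocol analysis informs the model. The within-trial ITT economic analysis is kept. A reader might infer that the whole economic conclusion rests on per-protocol data, or that the extrapolated figure is the one commissioners will use. The protocol says neither.
- **The direction is not certain.** A reader might infer that per-protocol input must flatter NMES. Adherers also use more sessions, sessions are costed, and cases 4, 6 and 7 show equality or reversal.
- **The size is not 1/adherence.** It is tempting to say that the QALY gain is inflated, and the cost per QALY deflated, by 1/0.47 = 2.13. That needs adherers and non-adherers to cost the same, which conflicts with per-session costing. In case 1 the gain is 2.13 times larger but the cost is also 590/383.30 = 1.54 times larger, so the cost per QALY differs by 40,777/29,500 = 1.38-fold. Nor is the 47% a proportion of patients who adhere to NMES, and the trial session before randomisation in section 8.4 may improve adherence.
- **Exclusions need not fall in one arm only.** With no definition of the set, and crossovers to be recorded under section 11.3.2, control participants might be excluded as well.

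The strongest remaining argument is that a model can take the effect in those treated as one input and handle uptake and adherence as separate parameters. Session counts (section 3.3.2) and delivery costs (section 8.13.1) will be collected, and model structure commonly belongs in a later analysis plan. But the protocol describes no such structure, and modelling adherence separately would not restore the randomised comparison in the effect input. The choice of analysis set is something the protocol does fix.

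**Conclusion.** The point holds in a limited form. Section 8.13.2 commits the beyond-trial model to a non-randomised contrast in an undefined population and states no ITT counterpart. That conflicts with the purpose of the economic objective and with the ITT principle used for the clinical primary analysis. The loss of randomisation and the mismatch with the population offered NMES hold whichever way the error runs.

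An error in favour of NMES is likely, because set-up costs are spread over a larger average effect and adherers tend to do better, but it is not assured. The size is unknown: it depends on set-up and session costs, NMES adherence and the shape of the dose-response, none of which the documents give. The ratios in the table illustrate that dependence and are not estimates for this trial. Only the extrapolated cost per QALY is affected. The amendment is worth making, but the matter does not threaten the trial.

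**What to change.** Amend the sentence in section 8.13.2 so that the ITT cost and QALY differences are the base case for the beyond-trial model. Keep per-protocol inputs as a labelled scenario analysis, with the per-protocol population defined in advance for both arms. Carry the same wording into any health economics analysis plan.

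No new data are needed and the per-protocol result is not lost. The cost is slightly more analysis work, and an extrapolated cost per QALY that may look less favourable to NMES.

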8.14 Withdrawal criteria

It will be clearly stated in both the PIS and the consent form that the participant is free to withdraw from the study at any time for any reason without prejudice to future care, and with no obligation to give the reason for withdrawal.

If a participant withdraws from the study, or loses capacity to consent, data and samples that have been collected up until the point of withdrawal/loss of capacity will be retained and used in the study.

8.15 End of study

The end of the study will be defined as the point at which all data has been collected and analysed.

9. STORAGE AND ANALYSIS OF CLINICAL SAMPLES

9.1 Arrangements for sample collection

Plasma collection

Venous blood collected from the dialysis line from will be collected into a tube containing EDTA or sodium heparin, centrifuged at 1500g for 10 minutes at 4°C The resulting plasma will be stored at -80 °C in 1ml aliquots. Samples will be analysed at the University of Leicester or Loughborough University.

Serum collection

Venous blood collected from the dialysis line from will be collected into plain tubes and left at room temperature for 10 minutes to clot. The sample will then be centrifuged at 2500g for 15 minutes at room temperature. The resulting serum will be stored at -80 °C in 1ml aliquots. Samples will be analysed at the University of Leicester or Loughborough University.

Peripheral mononuclear blood cell (PBMC) collection

PBMCs will be isolated from whole blood using the Ficoll-Paque Density Centrifugation method. Isolated PBMCs will be stored at -80 °C until needed. Samples will be analysed at the University of Leicester or Loughborough University.

Skeletal muscle biopsies

Muscle biopsy samples (approx. 100mg) will be treated depending upon the downstream analysis. A portion of the tissue will be immediately be stored in liquid nitrogen, in RNAse later at -80°C, in electron microscopy fixative, glutaraldehyde, or placed in frozen in chilled isopentane and subsequently stored in liquid nitrogen or embedded in resin. Samples will be analysed at the University of Leicester or Loughborough University.

9.2 Arrangements for sample analysis

Plasma and serum samples will be analysed locally at the University of Leicester, or Loughborough University. We may require samples to be sent to a commercial company for more detailed analysis of proteins (e.g. cytokines) that we are unable to perform in house.

Skeletal muscle samples will be analysed locally at the University of Leicester, or at Loughborough University. If samples are to be sequenced for RNA or microRNAs, this will be performed by a commercial company.

If any sample remains after analysis has been completed and the individual has consented to their samples being retained, we will continue to store the sample for use in future studies that gain ethical approval or enter the sample into a tissue bank. A clause will be added into the consent form to this effect. If participants do not consent to this, any remaining sample will be destroyed after analysis. Samples may be analysed straight away, or stored appropriately until analysis at a later date.

9.3 Storage arrangements for samples

Samples will be stored in laboratories at the University of Leicester and Loughborough University. Samples will be placed under storage conditions as soon as possible after collection. Samples will be stored at each site and transferred to the relevant laboratory in batches every 3-4 months.

With participants' consent, samples remaining following analysis will be retained for future research and following closure of the study, will be transferred to a registered research tissue bank.

9.4 The destruction arrangements for samples

With participants' consent, any tissue remaining at the end of this study will be transferred to a tissue bank. If participants do not consent to this, any remaining samples will be destroyed under witness at a local incineration facility. Any sample destruction will be carefully documented.

It is the responsibility of the study site to ensure that samples are appropriately labelled in accordance with the study procedures to comply with the Data Protection Act. Biological samples collected from participants as part of

this study will be transported, stored, accessed and processed in accordance with national legislation relating to the use and storage of human tissue for research purposes and such activities shall at least meet the requirements as set out in the 2004 Human Tissue Act.

10. SAFETY REPORTING

10.1 Definitions

10.1 Definitions	
Term	Definition
Adverse Event (AE)	Any untoward medical occurrence in a patient or clinical investigation participants, which does not necessarily have to have a causal relationship with this treatment. An AE can therefore be any unfavourable and unintended sign (including an abnormal laboratory finding), symptom or disease temporally associated with the study, whether or not considered related to the study.
Adverse Reaction (AR)	An untoward and unintended response in a participant to an investigational medicinal product which is related to any dose administered to that participant. The phrase "response to an investigational medicinal product" means that a causal relationship between a trial medication and an AE is at least a reasonable possibility, i.e. the relationship cannot be ruled out. All cases judged by either the reporting medically qualified professional or the Sponsor as having a reasonable suspected causal relationship to the trial medication qualify as adverse reactions. It is important to note that this is entirely separate to the known side effects listed in the SmPC. It is specifically a temporal relationship between taking the drug, the half-life, and the time of the event or any valid alternative etiology that would explain the event.
Serious Adverse Event (SAE)	A serious adverse event is any untoward medical occurrence that: • results in death • is life-threatening • requires inpatient hospitalisation or prolongation of existing hospitalisation • results in persistent or significant disability/incapacity • consists of a congenital anomaly or birth defect Other 'important medical events' may also be considered serious if they jeopardise the participant or require an intervention to prevent one of the above consequences. NOTE: The term "life-threatening" in the definition of "serious" refers to an event in which the participant was at risk of death at the time of the event; it does not refer to an event which hypothetically might have caused death if it were more severe.
Serious Adverse Reaction (SAR)	An adverse event that is both serious and, in the opinion of the reporting Investigator, believed with reasonable probability to be due to one of the trial treatments, based on the information provided.
Suspected Unexpected Serious Adverse Reaction (SUSAR)	A serious adverse reaction, the nature and severity of which is not consistent with the information about the medicinal product in question set out in the reference safety information: • in the case of a product with a marketing authorisation, this could be in the summary of product characteristics (SmPC) for that product, so long as it is being used within its licence. If it is being used off label an assessment of the SmPCs suitability will need to be undertaken. • in the case of any other investigational medicinal product, in the investigator's brochure (IB) relating to the trial in question

